6.2 Method for Assigning Subjects to Treatment Groups

No randomization schemes will be employed; all subjects will receive the same starting dose of sebelipase alfa in this study.

Each subject will be assigned an enrollment number after informed consent has been obtained from the subject's parent or legal guardian. This enrollment number will be used to identify the subject throughout his/her participation in the study.

A subject who does not meet all study eligibility criteria due to a potentially transient condition observed at screening (e.g., discontinuation of another investigational medicinal product within 14 days) will be allowed to return for re-screening.

6.3 Storage and Disposition of IMP

6.3.1 Receipt of IMP

Upon receipt of the IMP, an inventory must be performed and verified. It is important that the designated study staff counts and verifies that the shipment contains all the items noted in the shipment inventory. Any damaged or unusable IMP in a given shipment will be documented in the study files. The Investigator must notify study Sponsor of any damaged or unusable IMP that was supplied to the Investigator's site.

6.3.2 Storage

Vials of sebelipase alfa must be stored under controlled refrigerated conditions at 2°C to 8°C (36°F to 46°F). Vials should not be frozen and will be protected from light during storage. Temperature monitoring must be performed by the investigational site to ensure proper storage of sebelipase alfa throughout the study. Refer to the IMP manual for instructions on how to handle temperature excursions.

The infusion bag (or syringe) containing sebelipase alfa will be prepared just prior to infusion administration. The prepared infusion, diluted in 0.9% Sodium Chloride Injection, may be stored at room temperature (20°C to 25°C) for no more than 12 hours, although it is preferable that prepared solution be used within 4 hours of dilution. Shaking or other forms of agitation must be avoided.

6.3.3 Disposition

The Investigator or designated person (e.g. a licensed pharmacist) will be responsible for maintaining accurate records for all IMP used. Opened sebelipase alfa vials still containing any residual volume may be stored at room temperature for IMP accountability. Following IMP accountability, the Sponsor or designee will give written authorization to the Investigator to return or destroy any remaining IMP as instructed.

6.4 Preparation and Administration of IMP

6.4.1 Preparation of IMP

The infusion bag (or syringe) containing sebelipase alfa will be prepared just prior to the start of infusion administration. Prior to preparation of the infusion, the vials of study drug will be visually inspected. The solution should not be used if it contains foreign particulate matter or is discolored. The solution may be used if a small number of visible translucent to opalescent or white amorphous or threadlike particles are present in the vial. The contents should NOT be warmed using a microwave or other heat source. Sebelipase alfa is a protein and will be handled and mixed gently to prevent foaming.

If subject's weight cannot reliably be obtained on the morning of the infusion then the subject's most recent weight measurement within 7 days, rounded to the nearest 0.1 kg, will be used for calculating the volume of study drug to be withdrawn from the vial(s) to prepare the infusion.

Sebelipase alfa should be diluted to a concentration of 0.1 to 1.5 mg/ml for infusion. Refer to the IMP manual for detailed instructions regarding preparation

6.4.2 Administration of IMP

Study drug should not be infused with other products in the same infusion tubing as the compatibility of sebelipase alfa in solution with other products has not been evaluated.

It is required that all infusions of study drug be administered using in-line filtration with a low-protein binding 0.2- μ filter. Occlusion of the in-line filter may occur, which is not uncommon with IV infused proteins. Studies of sebelipase alfa with several commercially available 0.2- μ filters have shown that the IV line occlusion is primarily attributed to the surface area of the filter. Since several 0.2- μ filters are available at both 0.45 cm² and 10 cm², it is recommended to contact the filter manufacturer to determine the surface area of the 0.2- μ filter that is being used if occlusion of the in-line filter occurs. In this situation, a larger surface area 0.2- μ filters will be used.

The IMP infusion will be administered at an infusion rate depending on the subject's weight, and must be administered under close supervision of the Investigator, or designee. Sebelipase alfa should not be administered at an infusion rate exceeding 4 ml/kg/hr. Refer to the IMP manual for detailed instructions regarding administration.

6.5 Blinding of IMP

This is an open label study with no requirement for blinding.

Page 43 of 66

6.6 Destruction of IMP

Following IMP accountability and written permission from the Sponsor to destroy IMP, documentation of destruction must contain, at a minimum, the following:

- 1. Identity, lot number or subject number
- 2. Quantity
- 3. Date of destruction
- 4. Method of destruction
- 5. Name and signature of person or company responsible for destruction

7 Assessment of Safety

The methods for collecting safety data are described below. All personnel involved with the study must ensure they are familiar with the content of this section.

7.1 Adverse Events and Laboratory Abnormalities

7.1.1 Clinical Adverse Events

An *Adverse Event* is any untoward medical occurrence in a subject, which does not necessarily have to have a causal relationship with the administration of a study drug. An AE can therefore be any unfavorable and unintended sign, symptom, or disease temporally associated with the use of the study drug, whether or not considered related to the medicinal product. Pre-existing conditions that worsen in severity during the course of the study are to be reported as AEs.

All AEs occurring during the clinical study will be reported on the AE page of the CRF as described in Section 7.3.

The Investigator will assess the severity, causality (relationship to study drug), and seriousness of each AE.

Severity: The Investigator will assess the severity of all AEs/SAEs as mild, moderate, or severe based on the following definitions (developed from Clinical Data Interchange Standards Consortium Study Data Tabulation Model standard terminology v3.1.1).

- Mild: A type of AE that is usually transient and may require only minimal treatment or therapeutic intervention. The event does not generally interfere with usual activities of daily living.
- Moderate: A type of AE that is usually alleviated with additional specific therapeutic
 intervention. The event interferes with usual activities of daily living, causing discomfort,
 but poses no significant or permanent risk of harm to the research participant.
- **Severe:** A type of AE that interrupts usual activities of daily living, or significantly affects clinical status, or may require intensive therapeutic intervention.

Causality: AEs will be assessed as not related, unlikely related, possibly related, or related to study drug. Table 3 provides general guidance on the assessment of causality. For data reporting purposes, AEs assessed as not related or unlikely related will be classified as unrelated to study drug, and AEs assessed as possibly related or related will be classified as related to study drug. Assessment of causality should be based on the Investigator's medical judgment and the observed symptoms associated with the event.

Table 3: Assessment of Causality

Table 6. Assessment	· · · · · · · · · · · · · · · · · · ·
Relationship to IMP	Criteria for Judgment
Related	Reasonable temporal relationship of the clinical event to study drug administration AND cannot be reasonably explained by other factors (such as the subject's clinical state, concomitant therapy, and / or other interventions).
Possibly Related	The temporal relationship of the clinical event to study drug administration makes causal relationship possible but not unlikely AND other drugs, therapeutic interventions or underlying conditions do not provide a sufficient explanation for the observed event.
Unlikely Related	The temporal relationship of the clinical event to study drug administration makes causal relationship unlikely but not impossible AND other drugs, therapeutic interventions or underlying conditions provide a plausible explanation for the observed event.
Not Related	Data are available to clearly identify an alternative cause for the reaction.

Seriousness: AEs will be classified as serious or non-serious according to the definitions provided below.

A **serious adverse event** is any AE that results in any of the following outcomes:

- Death
- Immediately life threatening
- Requires inpatient hospitalization or prolongation of existing hospitalization
- Results in congenital anomaly/birth defect
- Persistent or significant disability or incapacity
- An important medical event that may not result in death, be life threatening, or require
 hospitalization may be considered an SAE when, based upon appropriate medical
 judgment, the event may jeopardize the subject and may require medical or surgical
 intervention to prevent one of the outcomes listed

All AEs that do not meet any of the criteria for serious, should be regarded as **non-serious adverse events**. Given the severity and life threatening nature of LAL Deficiency in infants, it is plausible that some pediatric subjects will be hospitalized during the first several weeks on study. Continuation of this initial hospitalization for participation in the trial is not considered an SAE. Also, a hospitalization to accommodate a study procedure is not considered an SAE. However, during the hospitalization, adverse events will be collected and assessed for seriousness & reported appropriately (i.e., Important medical event or prolonged hospitalization).

All SAEs and IARs must be reported to the Sponsor as described in Section 7.4.

Page 45 of 66

7.1.2 Laboratory Test Abnormality

Laboratory test results will be recorded, or appear on the laboratory reports submitted directly from the central laboratory. Out of range laboratory test values should not be reported as AEs UNLESS they are considered to be clinically significant abnormalities by the Investigator.

7.1.3 Adverse Events of Special Interest (Infusion-Associated Reactions)

Infusion-associated reactions (IARs) will be considered AEs of special interest. Any AE that occurs during the infusion or within 4 hours after the infusion is completed and is assessed by the Investigator as at least possibly related to study drug will be designated as an IAR. In addition, if, at any time during the study, the Investigator observes symptoms that he/she considers to be consistent with an IAR or hypersensitivity reaction related to administration of study drug, the symptoms should be recorded as an AE(s) and designated as an IAR(s). Individual adverse event terms should be recorded rather than the terms, IAR or Infusion Associated Reaction.

As with any ERT, medications and equipment for the treatment of hypersensitivity reactions must be available for immediate use in case of unexpected, severe hypersensitivity reaction. These supplies include, but are not limited to, oxygen, acetaminophen, antihistamines (e.g., diphenhydramine, parenteral and oral), corticosteroids, epinephrine, and cardiopulmonary resuscitation devices.

General guidelines for classifying the severity of a reaction are provided in Appendix B.

For similar biological products, most acute IARs occur within 2 hours of the infusion. Signs of a possible acute IAR may include:

 Hyperemia, flushing, fever and/or chills, nausea, pruritus, urticaria, gastro-intestinal symptoms (vomiting, diarrhea, abdominal cramping), cardiopulmonary reactions, including chest pain, dyspnea, wheezing, stridor, hypotension or hypertension

If any of the above signs and symptoms are observed during the infusion and the subject remains hemodynamically stable:

- The infusion rate must be slowed (reduced to half the rate being given at the onset of the event, e.g., from 10 mL/hr to 5 mL/hr) and the infusion time extended in accordance with the institutional standard of care. The infusion rate may be decreased further by 25% if symptoms persist. Once the event has resolved, the infusion should continue for a minimum of 30 minutes at the reduced rate before the rate is increased to 75% of the original rate on the infusion schedule. If the subject tolerates the infusion at 75% of the original rate for at least 30 minutes the original rate may be restored for the remainder of the infusion.

7.2 Handling of Safety Parameters

7.2.1 Serious Adverse Events (Immediately Reportable to the Sponsor)

All SAEs and all IARs (serious and non-serious), irrespective of the treatment received by the subject, must be reported to the Sponsor or designee immediately and no later than 24 hours of the Investigator's first knowledge of the event (expedited reporting).

7.2.2 Adverse Event Reporting Period

The study period during which AEs must be reported is defined as the period from signature of the informed consent to the end of the study treatment follow-up. Adverse events occurring after signing the informed consent but prior to the first dose of study medication will only be recorded if assessed as related to protocol procedures or requirements. For this study, the study treatment follow-up is defined as a minimum of 30 days following the last administration of study treatment. If a subject experiences an SAE that is considered to be related to study treatment at any time after the study, it must be reported to the Sponsor.

7.2.3 Treatment and Follow-up of Adverse Events

During the study, all AEs and SAEs will be followed up until they have returned to baseline status or stabilized or until the Investigator and Sponsor or designee agree that follow-up is no longer necessary. If a clear explanation is established, it should be documented.

Treatment of AEs is at the discretion of the Investigator and should follow the standards of medical care at the Investigator's institution.

7.2.4 Follow-up of Abnormal Laboratory Test Values

In the event of unexplained clinically significant abnormal laboratory values, the tests should be repeated immediately and followed up until they have returned to baseline values and/or an adequate explanation of the abnormality is found. If a clear explanation is established, it should be documented.

7.2.5 Pregnancy

Subjects in this study will be of non-reproductive potential.

7.3 Recording of Adverse Events

At each contact with the subject (and the subject's parent or legal guardian), the Investigator must seek information on AEs by specific questioning and, as appropriate, by examination. Information on all AEs should be recorded immediately in the source documentation and in the eCRF. All clearly related signs, symptoms, and abnormal diagnostic procedures results should be recorded under one diagnosis.

AEs will be recorded from the time of signing of the informed consent until completion of the last scheduled visit, i.e., the follow-up visit. Adverse events occurring after signing the informed consent but prior to the first dose of study medication will only be recorded if assessed as related to protocol procedures or requirements. Any AEs remaining unresolved at the completion of the last visit should be recorded as ongoing. Ongoing AEs/SAEs should continue to be followed up for the period specified in Section 7.2.2 but without further recording in the eCRF. However, follow-up information on SAEs must be reported to the Sponsor or designee as described in Section 7.4.1. Any SAE that occurs after the study period and is considered to be related to the study treatment or study participation should be recorded and reported immediately.

Any AE that occurs within 24 hours of the infusion will be recorded by time and date, AEs occurring 24 hours after the infusion will be recorded by date only. The date and time, or the date when the AE started and stopped, as well as the intensity, seriousness, action taken with regard to the study treatment, causality assessment and outcome of the event will be recorded for each AE.

7.4 Reporting of Serious Adverse Events and Unanticipated Problems

Investigators and the Sponsor must conform to the AE reporting timelines, formats, and requirements of the various entities to which they are responsible. (§13 GCP-V; Detailed guidance on the collection, verification and presentation of adverse event/reaction reports arising from clinical trials on medicinal products for human use ['CT-3']; US CFR Title 21, §312.32, Investigational New Drug [IND] safety reporting). The Sponsor or designee will report all reportable events to all regulatory authorities, and Investigators as required by local regulations.

All SAEs and IARs, and other reportable events (see Section 7.4.3) must be reported to the Sponsor or designee in an expedited manner according to timelines described in Section 7.4.3. Periodic Safety reporting to regulatory authorities will be done by the Sponsor according to national and local regulations.

7.4.1 Investigator Reporting: Notifying the Study Sponsor

Any SAE, IAR, or unanticipated problem posing risk of harm to subjects, must be reported to the Sponsor, or designee immediately and no later than 24 hours of the Investigator's first knowledge of the event. To report such events, an SAE/IAR form must be completed by the Investigator and sent within 24 hours. The Investigator will keep a copy of this SAE or IAR form on file at the study site.

The Investigator must promptly provide further information on the SAE, IAR, or the unanticipated problem. This should include a copy of the completed SAE or IAR form, and any other information that will assist the understanding of the event. Significant new information on ongoing SAEs or IARs must be reported to the Sponsor or designee immediately and no later than 24 hours of the Investigator's knowledge. Report SAEs and IARs by phone, fax, or email to:

SAE Reporting: Europe and Asia Pacific

24-Hour Hotline: SAE Fax: Email:

North, Central and South America:

Hotline (Urgent Calls Only) 24-Hour Hotline:

Fax:

PPD PPD PPD

> ica: PPD PPD PPD

7.4.2 Investigator Reporting: Notifying the IRB/IEC

Unanticipated problems posing risks to subjects or others as noted above will be reported to the IRB/IEC according to local regulations. Copies of each report and documentation of IRB/IEC notification and receipt will be kept in the Investigator's study file.

7.4.3 Sponsor Reporting: Notifying the FDA and all Regulatory Authorities

The Sponsor is required to report certain study events in an expedited manner to the FDA, the European Medicine Authority, and to all country Regulatory Authorities where the study is being conducted. The following describes the safety reporting requirements by timeline for reporting and associated type of event:

- Immediately and within 7 calendar days
 - Any suspected adverse reaction that is associated with the use of the study drug, unexpected, and fatal or life threatening
 - o Follow-up information must be reported in the following 8 days

- Immediately and within 15 calendar days
 - Any suspected adverse reaction that is associated with the use of the study drug, unexpected, and serious, but not fatal or life threatening
 - Any finding from tests in laboratory animals that suggest a significant risk for human subjects including reports of mutagenicity, teratogenicity, or carcinogenicity
 - Any event in connection with the conduct of the study or the development of the IMP which may affect the safety of the trial subjects
 - Follow-up information must be reported within 15 calendar days

The Sponsor will comply with all additional local safety requirements, as applicable. Periodic safety reporting to competent authorities will be done by the Sponsor or designee according to national and local regulations.

7.4.4 Sponsor Reporting: Notifying Participating Investigators

It is the responsibility of the study Sponsor or designee to immediately notify all participating Investigators of any suspected AE associated with the use of the drug that is both serious and unexpected, as well as any finding from tests in laboratory animals that suggest a significant risk for human subjects.

7.5 Independent Safety Review Committee (SRC)

It will be the responsibility of the Principal Investigator to oversee the safety of the study at his/her site. Additional oversight of the subject safety in the study will be provided by an independent SRC composed of individuals with pertinent medical expertise, who will serve in advisory capacity to the Sponsor to provide an additional level of scrutiny to minimize the chance that clinical trial participants are exposed to unreasonable or unnecessary risks. The activities and composition of the SRC will be outlined in the SRC Charter which will be ratified during the initial meeting, prior to commencement of dosing of the study subjects. The SRC will be tasked with ongoing review of safety data in order to advise the Sponsor regarding continued dosing and dose escalation decisions for the study. These safety monitoring functions and the oversight of such activities will be distinct from the requirement for study review and IRB/IEC approvals.

Core members of the SRC will not participate in the trial as investigators or sub-investigators, as members of any team otherwise participating in the trial, or in any other capacity that may compromise their privileged activities on the SRC. Neither members of the SRC nor their immediate families will have a direct financial interest in the sponsor or an interest that is dependent of the outcome of the trial. To be considered for SRC membership, all candidates must disclose all actual or potential conflict of interest, including any financial interest in, or research activity on a competing product. SRC members will be compensated at an appropriate market rate for time spent reviewing, discussing, and attending the meetings. The sponsor will also reimburse SRC members for any out-of-pocket travel expenses required for attendance at the meetings. Aside from the above, SRC members will receive no additional compensation for their membership on the committee as outlined in the SRC Charter.

Page 50 of 66

8 Statistical Plan

The Sponsor or its designee will be responsible for data collection and editing, reviewing and validating all the information in the eCRFs, statistical analysis, and generation of the clinical study reports.

An analysis will be performed after all treated subjects have reached 12 months of age or have died or withdrawn from the study.

Final analyses will be performed after all subjects have completed treatment in the study (up to 3 years) or have died or withdrawn from the study.

8.1 General Considerations

All data will be presented in listings; summary tables and graphs will be provided, as appropriate. Unless otherwise noted, tabulations for efficacy endpoints will be presented for subjects in the Full Analysis Set (FAS). Descriptive summary statistics (n, mean, median, standard deviation, minimum and maximum) will be calculated for the continuous variables. Shift tables and/or frequencies and percentages will be produced for the categorical variables. When percentages are reported, the number of treated subjects will be used as the denominator, unless otherwise noted. As appropriate, 95% two-sided confidence intervals (CIs) will be calculated around the estimates based on the exact binomial distribution for binomial endpoints and the t-distribution for continuous endpoints.

Baseline will be defined as the last measurement prior to the first infusion of sebelipase alfa. (Note: For exploratory analyses, the first available measurement after initiation of treatment may be used as baseline if a pretreatment measurement is unavailable.) In order to facilitate comparison with literature, survival analyses will be presented with subject birth date as "time 0"; analyses of other endpoints over time will consider date of first dose as "time 0".

Details of the planned analyses and statistical methodologies will be provided in a separate Statistical Analysis Plan.

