#### 7.3.1.1. Overall Survival and Survival at 12, 18, 24 and 36 months of age

Survival will be analyzed as the proportion of subjects surviving to 12, 18, 24, and 36 months of age. A 95% exact confidence interval, calculated using the Clopper-Pearson method, will also be presented for each proportion estimate. In addition, the Kaplan-Meier estimate of median survival time and 95% confidence interval will be summarized as well as the number of deaths and the number and percentage of subjects censored. Kaplan-Meier curves of survival since birth and survival since first dose of SBC-102 will be presented. Kaplan-Meier estimates of median survival since first dose of SBC-102 will also be provided, along with 95% CIs, if estimable.

Survival rates and median age at death derived from this study will be compared to rates/times reported in the literature and previous studies. No statistical comparisons will be performed.

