#### 7.3.1.4. Anthropometric Parameters

Anthropometric indicators of growth will be plotted on standard growth curves. Z-scores and percentiles based on the age-gender standardized norms will be calculated in accordance with the methodology described by the WHO (subjects  $\leq 24$  months) or CDC (subjects > 24 months to 18 years) and using the growth charts relevant to the respective methodology. Summaries will include summaries of observed z-scores and percentiles at each visit and also the change from baseline and the percentage change from baseline (percentile data only). In addition, the percentages of subjects who meet criteria for underweight (<-2 standard deviations [SD] from the median for WFA), stunting (<-2 SD from the median for LFA/HFA), and wasting (<-2 SD from the median for WFL/WFH) will be tabulated for each time point.

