#### 9.4.2 Time to Death (from Birth)

Time to Death (months) = [(Date of Death - Date of Birth + 1)/365.25]\*12;

This derived variable will be used in the calculation of Kaplan-Meier estimate of median age at death/median survival since birth. This calculation will be adjusted for subjects born prematurely; details are described in Section 7.3.1.4.

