#### 9.4.3 Time to Death (from first Infusion of SBC-102)

Time to Death (months) = [(Date of Death - Date of First SBC-102 Infusion + 1)/365.25]\*12;

This derived variable will be used in the calculation of Kaplan-Meier estimate of median survival since first dose of SBC-102.

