#### 9.4.12.6 Denver II Developmental Screening Test (DDST)

The Denver II Developmental Screening Test (DDST) will be administered at the time points specified in the schedule of assessments.

The test is a standardized measure to assess development in children from 1 month to 6 years of age (Frankenberg et al., 1992). It includes performance-based and parent-reported items in 4 functional areas: fine motor-adaptive, gross motor, personal-social, and language skills with respect to the age-matched population. The test was normed on a diverse sample of children who were full term and had no obvious developmental disabilities; the norms indicate when 25%, 50%, 75%, and 90% of children passed each item. DDST II results are expressed as Normal, Abnormal, Questionable, and Untestable. The instrument has good inter-rater and test-retest reliability (correlations  $\geq$  0.90 for most tests).

The test must be administered by a trained clinician. Administration and scoring of DDST is based upon the child's age. (Note that for premature infants, the number of months premature is subtracted from the infant's chronological age.) For each test item administered, the clinician determines if the child's response falls within or outside of the normal expected range of success on that item for the child's age. The interpretation of the individual test items is then used to classify the child's development in each functional area and for the overall test.

Refer to the Study Operations Manual (SOM) for further information on administration and scoring of DDST.

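### Survival is timed from birth in children who had to be alive at first dose, so it is biased upward against literature that follows untreated infants from birth

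*Protocol*

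**What the plan says.** Protocol Section 8.1: "In order to facilitate comparison with literature, survival analyses will be presented with subject birth date as" time 0. Protocol Section 8.3 limits the Full Analysis Set to children who received some study drug, and exclusion criterion 2 in Section 4.4 allows first dosing up to 8 months of age. Protocol Section 4.6.2 replaces children who discontinue before dosing, so they do not enter the denominator.

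SAP 7.3.1.1 plans crude proportions alive at 12, 18, 24 and 36 months of age, and Kaplan-Meier curves from birth and from first dose. It continues: "Survival rates and median age at death derived from this study will be compared to rates/times reported in the literature and previous studies". It then adds: "No statistical comparisons will be performed".

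SAP 9.4.2 counts time to death from the date of birth, with no term for age at entry: "This derived variable will be used in the calculation of Kaplan-Meier estimate of median age at death/median survival since birth". It goes on: "This calculation will be adjusted for subjects born prematurely; details are described in Section 7.3.1.4". SAP 7.3.1.4 is the growth section, which opens: "Anthropometric indicators of growth will be plotted on standard growth curves". It has no prematurity rule. The only such rule is for the developmental test: "for premature infants, the number of months premature is subtracted from" chronological age (SAP 9.4.12.6; the same rule is in Protocol Section 5.1.12).

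SAP 9.4.3 defines the first-dose clock: "This derived variable will be used in the calculation of Kaplan-Meier estimate of median survival since first dose of SBC-102".

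**The concern.** A child who dies before dosing can never be counted, so every child in the analysis is alive from birth to first dose by construction. A plain from-birth analysis credits that interval as survival. Protocol Section 1.1.2 describes a disease that usually kills before 6 months of age, so the permitted entry window runs past the usual age at death. A literature series that follows untreated infants from birth includes the early deaths that the trial cannot include.

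Survival is the first-listed secondary objective of a single-arm study, and outside rates are its only yardstick. Reaching 12 months of age also triggers its own analysis and study report (Protocol Sections 8 and 12).

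The prematurity sentence is a separate defect in the same variable. It moves the origin away from the birth date fixed in Protocol Section 8.1, it is not listed among the changes in SAP 4.1, and it cannot be programmed from the section that it cites.

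**Working it through.** **Inputs from the documents.** Origin at birth (Protocol 8.1); dosed children only (8.3); entry up to 8 months (4.4); n up to 10 (8.2). The plan states no survival rate, so there is no figure of its own to reproduce.

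**Assumptions.** No drug effect. Literature followed from birth. Untreated survival S(t) is Weibull with S(6 months) = 0.05 to 0.20 and shape 1 (constant hazard), 2 (rising) or 0.7 (falling). Three entry patterns are used: uniform on 0-3 months; 1-8 months weighted by the chance of being alive; uniform on 1-8 months. The last is an upper bound, because Protocol 1.1.2 (admission typically by 2 months) and 3.2.2.1 point to early entry.

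**Formula.** A child first dosed at age a reaches 12 months with probability S(12)/S(a). The inflation is the mean of this over children, minus S(12).

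**Worked case: constant hazard, S(6) = 0.20.** λ = −ln(0.20)/6 = 0.268 and S(12) = 0.20² = 4.0%.

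- Entry 0-3: 0.04 × (e^{3λ} − 1)/(3λ) = 0.04 × 1.236/0.805 = 6.1%, or +2.1 points.
- Alive-weighted 1-8: 7 × 0.04 × λ/(e^{−λ} − e^{−8λ}) = 0.0751/0.648 = 11.6%, or +7.6 points.
- Uniform 1-8: 0.04 × (e^{8λ} − e^{λ})/(7λ) = 0.04 × 7.24/1.88 = 15.4%, or +11.4 points.

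**Inflation of 12-month survival, in points, for S(6) = 0.05 to 0.20:**

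| Hazard | S(12) from birth | Entry 0-3 | Alive-weighted 1-8 | Uniform 1-8 |
|---|---|---|---|---|
| Constant | 0.25% to 4.0% | +0.3 to +2.1 | +1.2 to +7.6 | +3.5 to +11.4 |
| Rising (2) | up to 0.16% | under +0.1 | up to +0.2 | up to +0.5 |
| Falling (0.7) | 0.8% to 7.3% | +1.8 to +6.2 | +5.4 to +16.8 | +10.4 to +21.5 |

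At later ages, with constant hazard and alive-weighted entry, the inflation is at most +1.5 points at 18 months, +0.3 at 24 and about 0 at 36.

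**Median age at death** (5th death of 10, simulated). With constant hazard the mean is 2.9 to 4.0, 4.1 to 6.0 and 6.0 to 7.2 months for the three entry patterns, against a true 1.4 to 2.6. That is +1.4 to +4.6 months. With rising hazard it is +0.2 to +2.6 months. The comparison lapses if the median is not reached: the chance of 6 or more of 10 alive is 38%, 63% or 97% if true survival on treatment is 50%, 60% or 80%.

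**If literature cases had to survive to a diagnosis at 1-3 months** (assumed; constant hazard), their 12-month survival is 0.7% to 6.9% and their median 3.5 to 4.6 months. The trial then differs by −0.1 to −0.8 points and about −0.6 months with entry at 0-3 months. With alive-weighted entry it differs by about +0.8 to +4.7 points (1.5 − 0.7; 11.6 − 6.9) and +0.6 to +1.4 months.

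**Does delayed entry remove the bias?** In 1,000,000 simulated births (constant hazard, S(6) = 0.10, 0.25, 0.40, dosing ages uniform on 0-8 months, survivors to dosing kept), crude 12-month survival was 3.2%, 13.8% and 27.7%. The true values were 1.0%, 6.25% and 16.0%. With entry at age at first dose the estimates were 0.97%, 6.2% and 16.0%.

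**Invented illustration, n = 10.** First doses at 1, 1.5, 2, 3, 3.5, 4, 5, 6, 7 and 8 months. The child dosed at 1 month dies at 2.5, and the child dosed at 3 months dies at 4.5. Crude 12-month survival is 8/10 = 80% (exact 95% CI 44% to 97%). At 2.5 months 3 children are at risk, and at 4.5 months 5 are, so delayed entry gives (1 − 1/3)(1 − 1/5) = 53% (log-log 95% CI 7% to 86%).

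**The case against.** The strongest reply is that the bias is probably small here. Early admission and a progressive course suggest a rising hazard. Constant hazard would mean 42% to 63% dead by 2 months, and falling hazard 53% to 75%, which fits poorly with admission at about that age. With a rising hazard the 12-month inflation is at most 0.5 points. Early dosing, including of infants with an affected sibling, shrinks it further, and one child in 10 is 10 points. This largely stands for the 12-month proportion. It does not remove the shift in the median.

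The literature may also be conditioned on survival to diagnosis, which can reverse the sign, and case mix may differ. Both stand, and they are reasons for the SAP to say how the literature cases were ascertained.

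A first-dose Kaplan-Meier analysis is planned, the disposition listing gives age and first-infusion date (SAP 7.1.1), the comparison is descriptive, and no decision rule depends on it. These points limit the consequence. The first-dose curve has no guaranteed time, but it does not repair the proportions at fixed ages or the median age at death.

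The corrections are themselves fragile. In simulated null trials of 10, over all three hazards, the delayed-entry curve fell to zero with children still alive or yet to enter in 1% to 25% of runs (entry 0-3), 12% to 28% (alive-weighted) and 20% to 71% (uniform). In an assumed 30-infant series only 0.2 to 4.2 infants would be expected alive at 8 months, so an age-conditioned benchmark fails for late entrants. If slower-progressing children enter later, both corrections overshoot; in the frailty scenarios tried, the benchmark was 1.8 to 4.2 points too high. This stands, so the corrections can only supplement the crude results.

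**Conclusion.** The concern holds, conditionally: against literature that follows untreated infants from birth, the survival-to-dosing component is always upward. With 80% to 95% mortality by 6 months and constant hazard, 12-month survival gains between 0.3 and 11.4 points depending on entry ages, and the median gains 1.4 to 4.6 months. A rising hazard, which suits the disease description better, leaves mainly the median shift of 0.2 to 2.6 months. Against literature conditioned on diagnosis the bias is smaller and may be slightly negative; against earlier treated studies its direction depends on entry ages.

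The bias alone cannot plausibly produce 8 or more of 10 alive at 12 months within these assumptions: the probability is about 0.1% in the worst scenario. The limit depends on the assumed mortality. At 60% mortality by 6 months, falling hazard and uniform entry, the probability is about 4.4%, and the rising-hazard inflation reaches 2.8 points.

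This should be fixed, though no formal inference depends on it. The SAP 9.4.2 prematurity defect needs no assumptions: the cited section has no rule, and the sentence conflicts with the origin in Protocol 8.1.

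**What to change.** In SAP 7.3.1.1:

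1. Keep the crude 12-, 18-, 24- and 36-month proportions and the from-birth curve, and list age at first dose beside each child's survival outcome.
2. Where a literature series gives survival by age with enough infants at risk at the children's first-dose ages (set the minimum in advance, for example 5), compare the proportion alive at age t with the mean over children of S_lit(t)/S_lit(age at first dose). Otherwise state that the comparison is biased upward if the series follows infants from birth, and say whether its cases had to survive to diagnosis.
3. Add, as a supplementary display, a from-birth Kaplan-Meier curve in which each child joins the risk set at age at first dose, with numbers at risk. Note that it is unstable with at most 10 children and can drop to zero early.
4. State that items 2 and 3 assume age at first dose is unrelated to prognosis, and that the median comparison applies only if the median is reached.

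In SAP 9.4.2, reconcile the prematurity sentence with Protocol 8.1. Either use unadjusted chronological age for the survival results compared with literature, or write out the adjustment rule and show the unadjusted result beside it.

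The cost is SAP wording, one entry-time variable in the Kaplan-Meier program and one listing column; age at first dose is already derived (SAP Table 3). Item 2 also needs a literature survival-by-age curve to be found or digitised.
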